7.1.1.2. Study Disposition

The number of subjects who are enrolled, who have a clinical follow-up visit and who have imaging during the follow-up visit will be summarized. In addition, the number of subjects who complete the study or exit early will be summarized by reason.

Subject and Imaging accountability will be summarized in the following tabulated format up to 5-years (the example only provided up to 12-month):

	Subj	Subject Follow % (m/n) ¹			oject with Ima each time into % (m/n) ¹		Subjects with Adequate Imaging to Assess the Parameter % (m/n) ¹			Subject Events Occurring Before Next Visit ² n				
Implant and Follow-Up	Eligible ²		Imaging Follow- Up	CT/MR Imaging	Chest X-Ray	Additional Imaging Modalities	Max Aneurysm Diameter		Enrolled but not Implanted	Conversion to Surgery	Death	Withdrawal	Lost to Follow-Up	Not Due for Next Visit
Implant	9													
Events Between Implant and 1-Month									0	0	0	0	0	0
1-Month	9	100.0% (9/9)	100.0% (9/9)	88.9% (8/9)	77.8%(7/9)	0.0% (0/9)	88.9% (8/9)	88.9% (8/9)						
Events Between 1-Month and 6-Months										0	0	0	0	2
6-Months	7	100.0% (7/7)	100.0% (7/7)	100.0% (7/7)	100.0% (7/7)	100.0% (7/7)	100.0% (7/7)	100.0% (7/7)						
Events Between 6-Months and 12-Months										0	0	0	0	5
12-Months	2	0.0% (0/2)	0.0% (0/2)	0.0% (0/2)	0.0%(0/2)	0.0% (0/2)	0.0% (0/2)	0.0% (0/2)						
	Total 0 0								0	0	0	0		
	Deaths Post Conversion to Surger								sion to Surgery	0				
	Total Deaths								0					

7.1.2. Clinical Investigation Plan (CIP) Deviations

All enrolled subjects will be analyzed and reported based on evaluable data. Major and minor protocol deviations will be tabulated.

7.1.3. Analysis Set

All safety and effectiveness analyses will be performed on all enrolled subjects, according to the intention-to-treat (ITT) principle. The subject will be considered enrolled after arterial access is achieved and the Valiant Mona LSA Thoracic Stent Graft System has been introduced into the vasculature.

VML_Eval Statistical Analysis Plan **Form** Medtronic Revision [6.0] Page 14 of 27

General Methodology

Data collected from the clinical study will be analyzed as specified in the following sub-sections. Subject data listings, tabular, and graphical representations will be provided. In general, for categorical variables, frequency and percentage will be presented as descriptive statistics. For continuous variables, number of observations, mean, standard deviation, median, minimum, and maximum will be reported.

All key study endpoints will be presented with the point estimate and the corresponding 2-sided 95% confidence interval. Confidence intervals will be included in the final clinical study report, but may not be included in other reports, such as annual progress reports.

7.2.1. Study Day

Assessments will be presented chronologically by study day, which is defined in the following:

Study day = assessment day - date of index-procedure.

Study day will be calculated from the date of index procedure, i.e. Day 0. Day 1 is the day immediately after the initial implantation. Study day of an event which occurs prior to Day 0 will be presented as a negative number, if any.

Events occurring on the day of discharge will be considered in-hospital.

7.2.2. Duration of Follow-up

If a subject is not expired, then duration of follow-up will be calculated from the last date of follow-up visit or the final assessment as indicated on the Study Exit CRF, whichever is later. If a subject is expired, then the duration of follow-up will be calculated using the date of death. If a subject withdraws from the study, the duration of follow-up will be calculated using the date of withdrawal. Data except death, if any, reported after the date of withdrawal will be excluded from reporting.

Time Window of an Event or Assessment 7.2.3.

For events that can occur or are observed at any time during the study, such as an adverse event or death, no time window will be applied. For other events, an event that occurs "within 1 month" is an event that takes place between Days 0 to 30, inclusive. Similarly, an event that occurs "within 1 year" is an event occurring between Day 0 to Day 365, inclusive.

For visit-related or imaging based assessments, such as a CT scan, MRI, X-Rays, the analysis windows presented in Table 1 will be applied for by-visit data summaries:

Revision [6.0]

Page 15 of 27

Table 1. Time Window for Imaging Observations Analysis

Study Visit	Target Day	Scheduled Follow-Up Window	Analysis Window for Imaging Observations
Implant	0	Day 0	0
Discharge	n/a	n/a	1-14 Days
1 Month	30	15-45 Days	15-122 Days
6 Months	183	153-239 Days	123-270 Days
12 Months	365	335-421 Days	271-480 Days
24 Months	730	674-842 Days	481-913 Days
36 Months	1095	1039-1207 Days	914-1278 Days
48 Months	1460	1404-1572 Days	1279-1644 Days
60 Months	1825	1769-1937 Days	1645-2008 Days

Imaging based analyses will follow a "worst case" principle where any 'positive' finding of an undesirable outcome (e.g., fracture) or the worst measure (e.g., aneurysm diameter) in the analysis window will be used. If there are 2 or more assessments of the same subject for the same type of event within the same time window, then the following rules are applied:

- 1. If there are 2 or more positive findings on evaluable images for the same type of event for the same subject in the window, the earliest image showing a positive finding will be used to determine that the subject had an event in the window and this subject is only counted once for this type of event in this window.
- 2. If there is no positive finding for the event, the latest evaluable image showing no event will be used for analysis.

This process should be followed for each outcome, such that different images may be used for reporting on each outcome unless otherwise specified.

Table 2 shows which imaging outcomes are visible (marked with an "X") or invisible (not marked with an "X") using various imaging types. Evaluable images are images marked as "X" in the imaging matrix (Table 2) and a having response to "Was there evidence of <imaging outcome>?" of "Yes" or "No".

Revision [6.0]

Page 16 of 27

Images defined as 'Invisible' in the imaging matrix or any imaging assessment where the response to "Was there evidence of <imaging outcome>?" is "Not Applicable", "Not Evaluable", or blank/missing are not considered evaluable for imaging outcome analysis and are excluded.

Table 2. Imaging Matrix

Imaging Type	Migration	Endoleak	Device Integrity	Aneurysm Size Assessment	BSG/LSA Patency	MSG Patency
CTA or MR with Contrast	Х	Х	Х	Х	Х	Х
CTA or MR without Contrast	Х		Х	х	Х	Х
Chest Radiograph	Х		Х			
Doppler US					Х	

7.2.4. Reporting Precisions

When applicable, P-values will be presented in the bio-statistical tables similar to what is displayed in the supporting statistical software analysis output (round to 3 decimal places for SAS output), if p-value >0.999, display as >0.999; if p-value < 0.001, then display as <0.001.

Percentages will be reported with exactly one decimal place, unless otherwise specified (e.g., in the Table, Listing, and Graphs Shell Specifications). Further discussions may be needed to determine the sensible display format if the percentage is less than 0.1% (e.g. if one decimal place rule is used for 0.04%, it will be displayed as 0.0% which is misleading); however, unless otherwise specified, two decimal places will be used.

For summary statistics, unless otherwise specified (e.g., in the Table, Listing, and Graphs Shell Specifications), means and medians will be displayed to one more decimal place than was determined above, dispersion statistics will have 2 more decimal places, and the minimum and maximum will be displayed to the same number of decimal places as the original data point defined in the Data Definition Table (DDT).

7.3. Center Pooling

No poolability analysis is planned for this study.

7.4. Handling of Missing, Unused, and Spurious Data and **Dropouts**

In general, imputation of missing data will not be performed for all analyses. However, in cases where the date of adverse event onset is incomplete, the 15th day of the known month or July 1st of the known year will be used unless that results in a date earlier than the date of index procedure, in which case the date of index procedure will be used. For study endpoints, missing data will be listed with subject numbers for review. The imputed AE onset date cannot be later than last known date in the study. For instances where the AE onset date is imputed after the last known date in the study, the last known date in the study will be used for the AE onset date.

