7.9.3. Additional Observations

7.9.3.1. Major Adverse Events and Major Clinical Events

The following observations will be assessed through clinical follow-up (office visit or phone contact):

- Major adverse events (MAEs) rates within 30 days of the initial or secondary procedures, including:
 - All-Cause Mortality
 - Myocardial Infarction
 - Paraplegia
 - Renal Failure
 - Stroke
 - Left Arm/Hand Ischemia
- Secondary endovascular procedures
- Rupture
- Conversion to surgery
- Surgical revascularization of the LSA
- **Paraparesis**

[figure not shown]
The rate of the above events will be calculated on the subject level, and for different reporting time points, the correspondent cutoff days will be used as shown in Table 3.

For each visit (or reporting time point), the event rate will be calculated as the proportion of the number of subjects with a certain event term over the number of evaluable subjects. The evaluable subjects at each reporting time point include all subjects who are enrolled by the snapshot date and

- 1) Had a clinical or safety event (e.g. MAE) within (on or before) the Reporting cutoff Days, or
- 2) Had a follow-up or days to last contact at or after the lower limit of the Reporting Window,

Revision [6.0]

Page 19 of 27

[figure not shown]
3) The Withdrawal Consent Date /Recorded Lost-to-Follow-up Date at or after the lower limit of the Reporting Window

'Days to MAE' (date of earliest MAE – date of index procedure) and 'Days to Last Contact' (date of last contact – date of index procedure) are usually used for the determination of the eligibility of the 'evaluable subject'. The last contact date will be calculated based on the information gathered from all available dates during the follow-ups.

Similarly, 'Days to any AEs' and 'evaluability' of any AEs will be determined with the same principle as described above.

- 1. For death, Use the date of death from the CEC form, if it is not available then use Date of Death from study exit form.
- 2. For withdrew ("Subject withdrew consent to participate in the study" or " Physician's decision to protect the welfare of the subject") or "Subject enrolled but not implanted, completed 1 month follow-up", use Date of Exit from study exit form.
- 3. For patients who exited study for LTF, complete FU, or other reason, use last known date in the study from:
 - 1) Adverse Event Form
 - (i) Date event started
 - (ii) Date of resolution
 - 2) Secondary Procedure Form: Date of secondary procedure

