7.9.4. Subset Analysis

Subset analyses of the primary safety and effectiveness observations will be created for the subjects enrolled with aneurysms, penetrating ulcers, or chronic Type B dissections. Descriptive statistics will be used to analyze the primary observations, additional observations, and periprocedural and discharge clinical utility measures.

7.10.Safety Evaluation

Any Adverse events (AEs or SAEs) other than MAEs will be summarized by relationship and time period. Relationship will be site-reported in 3 categories, device-related, procedure-related and aneurysmrelated. If an AE is in 2 or more categories, it will be included in both or all summaries. All SAEs will be summarized separately. All AEs will be coded according to the Medtronic Endovascular Dictionary.

The rate of any AE will be calculated for following time periods:

- 0-30 days
- 31-365 days
- 366-730 days
- 731-1095 days
- 1096 -1460 days
- 1461 1825 days

The event rate is determined by number of subjects who had the event during the time period divided by number of subjects at risk at the beginning of the time period, i.e. number of subjects who are still in the study at the beginning of the time period.

Unanticipated Serious Adverse Device Effects (USADEs), Unanticipated Adverse Device Effects (UADEs) and deaths will be provided in a listing. Device malfunctions and failures will be listed.

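### The rule for imputing an incomplete AE onset date has no cap at the event's own resolution date, so it can place onset after resolution and in a later reporting period (minor)

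*SAP*

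**What the plan says.** SAP 7.4 does not impute missing data in general but makes an exception for incomplete AE onset dates: "the 15th day of the known month or July 1st of the known year will be used". It sets two bounds.

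- Lower bound: if the imputed date falls before the index procedure, "in which case the date of index procedure will be used".
- Upper bound: "The imputed AE onset date cannot be later than last known date in the study". If it would be, "the last known date in the study will be used for the AE onset date".

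The upper bound belongs to the subject, not to the event. SAP 7.9.3.1 builds the last date from every form: "The last contact date will be calculated based on the information gathered from all available dates during the follow-ups". The Adverse Event Form contributes both the start date and the "Date of resolution". That is the only use the SAP makes of the resolution date. For subjects who died, 7.9.3.1 uses the date of death.

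Onset timing feeds three outputs: the primary safety composite at 0-30 days (7.9.1), days to MAE against the Table 3 cutoffs (7.9.3.1), and the AE periods in 7.10 ("The rate of any AE will be calculated for following time periods" 0-30, 31-365, 366-730 days and so on).

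**The concern.** Any imputation rule has to place onset somewhere within the unknown interval, and a mid-month or mid-year choice is a reasonable convention. The issue here is narrower. When the resolution date of the same event is known and lies before the imputed date, the rule returns an onset that the trial's own record shows to be impossible. The SAP already accepts that imputed dates must be plausible, since it bounds them on both sides, but it leaves out the one bound specific to the event.

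Errors of this kind run in one direction only, because the recorded event must have begun no later than it resolved. A proven 30-day event can therefore be counted after Day 30. Under the evaluability rules in 7.9.3.1 the subject stays in the 1-month denominator. An imputed onset beyond Day 30 implies a last known date beyond Day 30, which passes the Day 15 lower limit in Table 3. The event leaves the numerator, the subject stays in the denominator, and the 30-day rate is understated.

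**Working it through.** The SAP gives no figure on this point to reproduce, so the check applies its rule literally.

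**Inputs from the SAP.** The 15th or July 1, the index date as floor and the last known date as cap (7.4). Study day = date minus index date, with Day 0 the index procedure (7.2.1). Periods as in 7.10. Maximum enrolment 44 (section 6).

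**Assumptions.** The example dates, long follow-up (so the existing cap does not bind), and the lag from onset to resolution, for which the SAP gives no figure.

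**Step 1: largest possible error.** Resolution cannot precede the first day of the recorded month or year.
- Month known: 15 - 1 = 14 days.
- Year only: January 1 to July 1 = 181 days, or 182 in a leap year, so about six months.

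**Step 2: examples.**

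| Index | Onset recorded | Resolved | Imputed by 7.4 | Period by 7.4 | Period if capped at resolution |
|---|---|---|---|---|---|
| 10 May 2016 | June 2016 | 8 June 2016 (21 + 8 = Day 29) | 15 June (21 + 15 = Day 36) | 31-365 | 0-30 |
| 1 Mar 2016 | 2016 | 20 Mar 2016 (Day 19) | 1 July (31 + 30 + 31 + 30 = Day 122) | 31-365 | 0-30 |
| 1 Mar 2016 | 2017 | 10 Feb 2017 (Day 346) | 1 July 2017 (Day 487) | 366-730 | 31-365 |
| 5 June 2016 | June 2016 | 10 June 2016 (Day 5) | 15 June (Day 10) | 0-30 | 0-30 |

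All four imputed dates are impossible. The first three change period and the fourth does not.

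**Step 3: how many date combinations are affected.** Take every index date in a 365-day year and every true onset on Days 0-30, which gives 365 × 31 = 11,315 equally weighted combinations, with resolution = onset + lag. Count (a) imputed date later than resolution, and (b) case (a) with imputed day above 30 and resolution on or before Day 30.

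| Lag (days) | Month only: (a) | Month only: (b) | Year only: (a) | Year only: (b) |
|---|---|---|---|---|
| 0 | 46.0% | 11.1% | 49.6% | 45.5% |
| 3 | 36.2% | 7.0% | 48.8% | 40.7% |
| 7 | 23.0% | 3.0% | 47.7% | 34.5% |
| 14 | 0% | 0% | 45.8% | 23.9% |
| 21 | 0% | 0% | 43.8% | 13.7% |
| 30 | 0% | 0% | 41.4% | 1.3% |

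The month-only zeros are exact. Onset is on day 1 of the month or later, so a lag of 14 days puts resolution on the 15th or later. At a lag of 30 days with year only, (b) requires onset on Day 0 and an index date from January 1 to May 31: 151 / 11,315 = 1.3%. A leap year changes the figures by at most about 0.2 points.

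**Step 4: size of one moved subject.** 1/44 = 2.3%, exact 95% CI 0.1% to 12.0%. After the move, 0/44 = 0.0%, exact 95% CI 0.0% to 8.0%.

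**The case against.** The strongest reply is that the problem is rare and nothing formal depends on it. It needs an incomplete onset together with a known resolution date, for the same event, that precedes the imputed date. The larger shares in the working need onset recorded only to the year while resolution is recorded to the day, which is an unusual pairing. The SAP does not say how many onset dates are incomplete. The study is descriptive, with no hypothesis tests. This all stands, and it is why the point is minor.

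Several partial safeguards also exist.
- The resolution date is one source for the last known date, so the existing cap works when resolution is the subject's last recorded date.
- Mortality, one of four primary safety components, has its own date rule in 7.9.3.1 (the CEC form, then the study exit form).
- 7.4 has missing endpoint data listed by subject for review. A reviewer might notice a problem, but the listing gives no rule for changing the imputed date.
- Edit checks or programming specifications may catch such dates. The documents available neither show nor exclude them.

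Three stronger readings are tempting and not supported. A reader might infer multi-year errors because the cap can lie up to 5 years away, but the imputed date stays in the recorded month or year unless a bound moves it, so the limits in Step 1 hold. A reader might take the shares in Step 3 as the proportion of events that will be misdated. They are shares of date combinations under an assumed lag, and they vary strongly with that lag. A reader might also conclude that the primary safety result is materially biased, but without a count of incomplete dates the documents cannot show that.

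**Conclusion.** The point holds as a minor defect. As written, 7.4 can date a non-fatal AE after its recorded resolution, by at most 14 days with the month known or about six months with the year only. It can thereby move an event proven to lie within Day 0-30 out of that window, or any event past a Table 3 cutoff or into a later 7.10 period. No other section of the SAP supplies the missing bound.

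The effect per subject is 2.3 percentage points if all 44 are enrolled and evaluable. The overall effect is unknown and probably small. The share of Day 0-30 date combinations moved out runs from 11.1% down to 0% (month only) and from 45.5% down to 1.3% (year only) over lags of 0 to 30 days. Those ranges rest on equal weighting of dates, a fixed lag, and follow-up long enough that the existing cap does not bind.

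**What to change.** In SAP 7.4, replace the upper limit with a clause to this effect: the imputed onset date may not fall after the earlier of (i) the resolution date of the same event, when known, and (ii) the subject's last known study date as derived in 7.9.3.1, which for a subject who died is the date of death. If the imputed date exceeds that limit, use the limit. Keep the index procedure date as the lower bound. The cross-reference to 7.9.3.1 makes a separate date-of-death term unnecessary.

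The cost is one clause and one minimum in the derivation code, using a field already collected. 7.12 provides the amendment route before analysis. Events without a recorded resolution date are handled as now. It would also help to report the number of imputed onset dates, so that readers can see whether the rule mattered.

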7.5. Adjustments for Multiple Comparisons

Statistical hypothesis testing will not be performed for this study, therefore, no adjustments for multiple comparisons will be performed.

7.6. Demographic and Other Baseline Characteristics

All clinically relevant baseline variables will be summarized and tabulated. Descriptive statistics will be presented as follows:

- · Categorical variables, including binary variables, will be reported by giving the number and percentage of patients in each category.
- Continuous variables will be reported by presenting the number of observations, mean, standard deviation, median, minimum, and maximum of each variable.

For all chosen baseline variables, patients whose assessment cannot be determined will be omitted from the respective analysis.

7.7. Treatment Characteristics

Descriptive statistics (frequency and percentage for categorical variables and number of observations; mean, standard deviation, median, minimum and maximum for continuous variables) will be displayed for the periprocedural through discharge clinical utility measures.

7.8. Interim Analyses

No interim analysis, intended to alter the study sample size, are planned for this study.

7.9. Evaluation of Objectives

7.9.1. Primary Safety Observation

The primary safety observation of this study is a composite endpoint that consists of 1) Aneurysm Related Mortality, 2) Stroke, 3) Paraplegia, and 4) Left Arm/Hand Ischemia within 1 month (0-30 days) of index procedure. Descriptive statistics (frequency and percentage) will be calculated for the primary

safety endpoint and its component events. A two-sided 95% confidence interval for the primary safety endpoint and its component will also be calculated using the exact binomial method.

7.9.2. Primary Effectiveness Observation

The primary effectiveness observation is Treatment Success that is defined as successful delivery and deployment of the stent graft (deployment of the Valiant Mona LSA Thoracic Stent Graft System in the planned location with no unintentional coverage of other vessels, assessed intra-operatively, and the removal of the delivery system) and successful exclusion of the aneurysm while maintaining patency of the MSG and BSG at the 30 day visit. Descriptive statistics (frequency and percentage) will be calculated for the primary effectiveness endpoint. A two-sided 95% confidence interval will also be calculated using the exact binomial method.

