4.3.1. Primary Safety Observation

The following clinical outcomes will be collected for reporting. The initial reporting period will be all occurrences within 1 month (Day 0 - Day 30) from the index procedure. The outcome data will consist of:

- Aorta-Related Mortality
- Stroke
- Paraplegia
- Left Arm/Hand Ischemia

Primary Effectiveness Observation 4.3.2.

The primary effectiveness observation is treatment success (defined below) and will be captured within the initial reporting period of 1 month from the index procedure.

Treatment success is defined as:

Technical success, which is the successful delivery and deployment of the stent graft (deployment of the Valiant Mona LSA Thoracic Stent Graft System in the planned location with no unintentional coverage of other vessels, assessed intra-operatively, and the removal of the delivery system) and successful exclusion of the aneurysm/penetrating ulcer or primary entry tear while maintaining patency of the MSG and BSG at 30 day visit.

Additional Observations 4.3.3.

The following additional observations will be evaluated through the 30 day visit and at each follow up visit.

Major adverse events (MAEs) rates within 30 days of the initial or secondary procedures, including:

Form Medtronic

Revision [6.0]

Page 7 of 27

- All-Cause Mortality
- Myocardial Infarction
- Paraplegia
- Renal Failure
- Stroke
- Left Arm/Hand Ischemia
- Secondary endovascular procedures
- Secondary endovascular procedures for primary device failures (including Type I/III endoleaks, aneurysm expansion, aneurysm/aortic rupture, and BSG occlusion)
- Rupture
- **Endoleaks**
- Maximum aneurysm diameter change from baseline*
- Exclusion of aneurysm
- Exclusion of penetrating aortic ulcer (PAU)
- Stent graft patency
- Stent graft integrity
- Conversion to surgery
- Surgical revascularization of the LSA
- **Paraparesis**
- Adverse events including serious adverse events and device, procedure, and/or disease-related Adverse Events
- For CTBD, these additional observations will be evaluated:
 - Coverage of primary entry tear (exclusion of false lumen)
 - Extension of dissection (proximally or distally) with or without complications
 - Continuing or new false lumen (FL) perfusion
 - Primary intimal tear false lumen perfusion (PIT FLP)
 - Proximal aorta false lumen perfusion (PA FLP)
 - Distal aorta false lumen perfusion (DA FLP)
 - Proximal branch false lumen perfusion (PB FLP)
 - Distal branch false lumen perfusion (DB FLP)

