Scenarios for each possible combination of the component outcomes and the final endpoint assessment of success vs. failure are presented in Table 4. Since the exclusion of aneurysm is an assessment of success with two component events, if both component events are 'success' then the final composite endpoint will be 'success' (scenario 1); if at least one component event is 'failure' then the final composite endpoint is 'failure' (scenario 2,3,4,5 8); if one component event is success, but the other component event is missing due to unevaluable data, the final composite endpoint will be missing

Revision [6.0]

Page 22 of 27

(scenario 6,7); finally, if both components are missing then composite endpoint will be missing (scenario 9):

Table 4. Exclusion of Thoracic Lesion Scenarios

	1 st component	2 nd component even	Composite		
Scenarios	Absence of Type I or III Endoleak	1 st post-operative assessment of Maximum aneurysm/dissectio n/PAU diameter	assessment of Maximum aneurysm/dissection /PAU diameter at each scheduled visit	Absence of growth > 5 mm	endpoint of Exclusion of TAA/PAU
1	Success	evaluable	evaluable	Success	Success
2	Success	evaluable	evaluable	Failure	Failure
3	Failure	evaluable	evaluable	Success	Failure
4	Failure	evaluable	evaluable	Failure	Failure
5	Missing	evaluable	evaluable	Failure	Failure
6	Missing	evaluable	evaluable	Success	Missing
7	Success	Missing/evaluable	Evaluable/missing	Missing	Missing
8	Failure	Missing/evaluable	Evaluable/missing	Missing	Failure
9	Missing	Missing/evaluable	Evaluable/missing	Missing	Missing

Exclusion of Penetrating Aortic Ulcer (PAU)

Exclusion of penetrating aortic ulcer (PAU) is defined as the absence of a type I or III endoleak associated to the absence of growth > 5 mm of the maximum measurable aortic diameter at the level of PAU; the reference diameter is the diameter measured at the first post-operative imaging exam.

The rate of the exclusion of PAU will be calculated similarly to that of the exclusion of Aneurysm;

Exclusion of False Lumen (dissection)

Exclusion of false lumen (dissection) is defined as the exclusion of primary entry tear of dissection associated to the thrombosis of false lumen at the level of stent graft.

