7.9.3.4. Additional Dissection Specific Assessments

Additional dissection specific assessments include the following:

- Coverage of primary entry tear (exclusion of false lumen)
- Extension of dissection (proximally or distally) with or without complications
- Continuing or new false lumen (FL) perfusion
 - Primary intimal tear false lumen perfusion (PIT FLP)
 - Proximal aorta false lumen perfusion (PA FLP)
 - Distal aorta false lumen perfusion (DA FLP)
 - Proximal branch false lumen perfusion (PB FLP)
 - Distal branch false lumen perfusion (DB FLP)
- Aortic remodeling post-procedure as measured by:
 - o Change from baseline* in the maximum true lumen (TL) diameter over the length of the stent graft
 - Change from baseline* in the maximum false lumen (FL) diameter over the length of the stent graft
 - o Change from baseline* in the maximum total descending thoracic aortic diameter
 - FL thrombosis over the length of the stent graft
 - * The discharge computerized tomography angiogram (CTA) will be used as the baseline to assess aortic changes. If a discharge CTA is not performed then, the one month follow-up CTA will be used for baseline purposes.

The rate of the above endpoints will be calculated at the post-operative time point and at each scheduled follow-up and the calculation will be based on the number of subjects who had the event divided by number of implanted subjects under the Dissection indication who are evaluated for that event at the time point. The imaging endpoint analysis time window will be used to determine if an image assessment belongs to a respective time point and the reporting details can be found in section 7.2.3 (Table 1).

Thoracic dissection measurement over entire DTA and thoracic measures over endograft segment

If there are multiple images in a reporting window, the image with the largest maximum thoracic aortic centerline diameter over the entire DTA in the window will be used for reporting all related measurements (e.g., maximum thoracic aortic centerline diameter, maximum true lumen diameter, etc.)

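### SAP 7.9.1 and 7.9.2, which set the reported primary rates, do not match the endpoint definitions in 4.3.1 and 4.3.2

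*SAP*

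**What the plan says.** **Effectiveness.** SAP 4.3.2 defines Treatment Success as technical success together with "successful exclusion of the aneurysm/penetrating ulcer or primary entry tear while maintaining patency of the MSG and BSG at 30 day visit". SAP 7.9.2 gives the definition again in full, without referring back to 4.3.2, and there the exclusion element reads "successful exclusion of the aneurysm while maintaining patency of the MSG and BSG at the 30 day visit". The reported percentage and its two-sided 95% exact binomial interval are specified in 7.9.2.

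**Safety.** SAP 4.3.1 lists four outcomes over days 0 to 30, the first being "Aorta-Related Mortality". SAP 7.9.1 describes a "composite endpoint that consists of 1) Aneurysm Related Mortality, 2) Stroke, 3) Paraplegia, and 4) Left Arm/Hand Ischemia within 1 month". The window and the other three components agree. The supplied text defines neither mortality term and does not say that they are equivalent.

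**Who is analysed.** Section 7.1.3 puts all enrolled subjects into every safety and effectiveness analysis. Section 7.9.4 calls for the primary observations separately for aneurysms, penetrating ulcers and chronic type B dissections.

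**Dissection wording elsewhere.** Section 7.9.3.3 defines exclusion of the false lumen as "exclusion of primary entry tear of dissection associated to the thrombosis of false lumen at the level of stent graft". Sections 4.3.3 and 7.9.3.4 list "Coverage of primary entry tear (exclusion of false lumen") and name false-lumen thrombosis as a separate item.

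**The concern.** Each primary observation has two full definitions that differ, in current sections of one SAP revision, and no rule says which prevails. The narrower version of each stands in the section that a programmer would code from. The word aneurysm cannot simply be taken to mean any lesion, because 7.9.3.3 defines exclusion of an aneurysm, of an ulcer and of a false lumen separately.

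The study tests no hypothesis, so the reported rates and intervals are the result itself, and the rule for the numerator determines them. Dissection subjects are the ones least well served by 7.9.2, and 4.1 says that the dissection expansion subjects are enrolled to support a later premarket approval analysis. A definition settled after the data are seen would be hard to defend there.

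**Working it through.** The SAP gives no sample-size calculation, target rate or result, so there is no figure of its own to reproduce. The check is a comparison of the text, followed by arithmetic on how many subjects are touched.

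**1. Text side by side**

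| Element | Section 4.3 | Section 7.9 |
|---|---|---|
| Lesion to be excluded | aneurysm, penetrating ulcer or primary entry tear (4.3.2) | aneurysm (7.9.2) |
| Graft patency at the 30-day visit | main and branch grafts | same |
| Mortality component | aorta-related (4.3.1) | aneurysm-related (7.9.1) |
| Other safety components | stroke, paraplegia, left arm/hand ischemia | same |
| Safety window | days 0 to 30 | same |

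**2. Subjects without a literal criterion in 7.9.2**

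Inputs: up to 44 subjects (section 6); a floor of about 25% dissections (4.2); a first group of 18, then 5 more aneurysm or ulcer subjects whose safety data decide whether the dissection arm starts (7.1.1.1).

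- At the floor: 0.25 × 44 = 11 dissections.
- If the first 18 + 5 = 23 subjects include no dissections (assumed): 44 − 23 = 21, and 21/44 = 47.7%.
- If the dissection arm does not start, fewer than 11.
- Ulcer subjects come on top; their number is not given.

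**3. Illustration for Treatment Success**

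Assumptions not in the documents: 44 enrolled and 40 successes under 4.3.2, so 40/44 = 90.9% (95% Clopper-Pearson 78.3 to 97.5). The four failures are split as one dissection and three others when there are 11 dissections, and as two and two when there are 21.

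| Handling of dissections under 7.9.2 | 11 dissections | 21 dissections |
|---|---|---|
| Left out as not assessable | 30/33 = 90.9% (75.7 to 98.1) | 21/23 = 91.3% (72.0 to 98.9) |
| All counted as not meeting the criterion | 30/44 = 68.2% (52.4 to 81.4) | 21/44 = 47.7% (32.5 to 63.3) |

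Leaving them out mainly widens the interval. The second row is an outer bound.

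**4. The thrombosis question**

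Suppose one dissection subject has the entry tear excluded but no false-lumen thrombosis at 30 days. That subject succeeds under 4.3.2 but fails if the 7.9.3.3 definition is applied. The overall rate goes from 40/44 to 39/44 = 88.6% (75.4 to 96.2), a change of 1/44 = 2.3 points. Within the dissection subset the same subject is worth 1/11 = 9.1 or 1/21 = 4.8 points. The documents do not say how many such subjects to expect.

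**5. The mortality label**

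Suppose one death is aorta-related but not aneurysm-related, and is the only event among 44. The 4.3.1 wording gives 1/44 = 2.3% (0.1 to 12.0); the literal 7.9.1 wording gives 0/44 = 0% (0 to 8.0).

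**The case against.** The best defence is that 7.9.1 and 7.9.2 are shorthand. Section 4.3.2 gives the full criterion, and 7.9.4 requires a dissection subset that an aneurysm-only rule could not fill. The SAP also uses the word loosely elsewhere: 4.3.3 speaks of disease-related adverse events, and 7.10 speaks of aneurysm-related ones. This makes the intent likely, and it stands as a reason for modest severity. It does not remove the conflict, because 7.9.2 is written as a complete definition and nothing ranks it below 4.3.2.

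On mortality, the supplied protocol consists of page headers only, so either term may be defined in pages not seen. All-cause mortality (7.9.3.1) and the death listing (7.10) would show any death that the composite omits. Both points stand.

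On thrombosis, 7.9.3.3 sits among the additional observations, and neither 4.3.2 nor 7.9.2 refers to it. The link is the parenthesis in 4.3.3 and 7.9.3.4 that equates covering the tear with excluding the false lumen. That supports a request for clarification, not a prediction that programmers would diverge.

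A reader might also infer a fault in Table 4 of 7.9.3.3, whose columns mention dissection ("assessment of Maximum aneurysm/dissection /PAU diameter at each scheduled visit") while its result is labelled "endpoint of Exclusion of TAA/PAU". The documents do not support much there: the aneurysm and ulcer rates follow that table's approach, and dissection has its own definition just after it. Nor is missing data a general gap. Table 4 sets the outcome for missing components, and 7.4 rules out imputation and lists missing endpoint data by subject.

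**Conclusion.** Wrong as written, in both primary observations. Confidence is high for the wording mismatch and moderate for the thrombosis question. As worded, 7.9.2 does not fit about 11 of 44 planned subjects at the dissection floor, or about 21 if the first 23 include no dissections, plus an unknown number with ulcers. Fewer dissections are affected if that arm does not start. Each subject scored differently moves an overall rate by 2.3 points, if 44 are enrolled.

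Three stronger readings are tempting and are not supported:

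- That the plan means to fail or drop every dissection. Sections 4.3.2 and 7.9.4 point the other way, so the low rates in the second row of the illustration are not forecasts.
- That deaths will be missed from the safety composite. Without the protocol's definitions, it cannot be shown that any death would be classified differently.
- That the thrombosis question shifts the rate by a large amount. That needs a count of affected subjects, which the documents do not give.

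The study is descriptive, so no test, error rate or decision threshold changes.

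**What to change.** Amend the SAP before the analysis, as 7.12 allows:

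1. In 7.9.2, use the exclusion criterion of 4.3.2, and state that each subject is scored on the lesion treated.
2. In 7.9.1, use the mortality term of 4.3.1, after checking it against the protocol.
3. Add one sentence saying whether Treatment Success for dissections needs entry-tear exclusion alone or also false-lumen thrombosis. Report the other version as an additional observation.

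The cost is a few sentences. No new data should be needed, since entry-tear coverage, false-lumen perfusion and false-lumen thrombosis are already planned observations in 4.3.3. The downside is that a primary rate may come out slightly less favourable.
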